8.7.3. Interim Analysis

- When approximately the enrolled patients completed 50% of their visits (after Visit 3), an interim analysis for safety and efficacy will be conducted by an independent data monitoring committee. Serious adverse events will be monitored by the committee on an ongoing basis throughout the study.

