STATISTICAL CONSIDERATIONS	 The primary objective of CLEAR study is to assess the clinical efficacy of Leflunomide as first line therapy and as add-on therapy to other DMARDs (such as Methotrexate, Hydroxychloroquine, Sulfasalazine) with or without Steroids as measured by the mean relative change in Clinical Disease Activity Index (CDAI) and Health Assessment Questionnaire (HAQ Disability Index) among patients with active rheumatoid arthritis. Considering an alpha error of 5% using two-sided 95% CI of Wilcoxon signed-rank test and a study power of 80%, a sample of 332 patients will be required to detect an effect size of 0.158 between baseline and study endpoint, plus an expected drop-out rate of 20% during the 9 months observational study duration. Thus, a sample of 398 patients will be appropriate that rounded to 400 patients. Randomization method 						
	Not applicable.						
	Statistical methodologies:						
	- Descriptive analysis:						
	 Percent (%) distribution for all categorical variables and 						

	mean with (SD) and median (Minimum: Maximum) for				
	- Comparative analysis:				
	 Student t-test and One Way ANOVA to estimate the comparison between the treatment arms for the numerical variables (according to their distribution; non-parametric substitution tests could be used). 				
	 Paired t-test and repeated measure ANOVA test to estimate the change in numerical variables throughout the study visits (according to their distribution; non-parametric substitution tests could be used). Chi2 test (or Fisher's Exact test) for unpaired and McNemar's test for paired categorical variables. 				
	All tests will be performed on the 5% level of significance.				
	 Any deviation(s) from the original statistical plan will be described in the final report). 				
	 Procedure for accounting for missing, unused, and spurious data will be explained in the statistical analysis plan (SAP). 				
	Interim analysis				
	When approximately the enrolled patients completed 50% of their visits (after Visit 3), an interim analysis for safety and efficacy will be conducted by an independent data monitoring committee. Serious adverse events will be monitored by the committee on an ongoing basis throughout the study.				
	- Protocol planned date: June 2017				
	- First patient In (FPI): September 2017				
	- Last patient In (LPI): December 2017				
ESTIMATED DURATION	- Last patient Out (LPO): September 2018				

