8.7.2. Comparative Analysis

o Student t-test and One Way ANOVA to estimate the comparison between the treatment

Study Protocol: EVA_CLEAR_11022017 Version Number

arms for the numerical variables (according to their distribution; non-parametric substitution tests could be used).

- Paired t-test and repeated measure ANOVA test to estimate the change in numerical variables throughout the study visits (according to their distribution; non-parametric substitution tests could be used).
- Chi2 test (or Fisher's Exact test) for unpaired and McNemar's test for paired categorical variables.
- All tests will be performed on the 5% level of significance.
- Any deviation(s) from the original statistical plan will be described in the final report.

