9.2. Mode of Administration

Arthfree (Leflunomide 20mg)

Study Protocol: EVA_CLEAR_11022017

Dose: 1 tablet once daily, should be swallowed whole with sufficient amounts of liquids. The extent of Leflunomide absorption is not affected if taken with meals. Doses higher than 20 mg/day are not recommended. Improvement in the rheumatoid condition usually starts after 4 to 6 weeks and may further improve up to 4 to 6 months.

Loading dose: a tablet of Leflunomide 100 mg for three days. should be swallowed whole with sufficient amounts of liquids. The extent of Leflunomide absorption is not affected if taken with meals.

Due to the long half-life in patients with rheumatoid arthritis and recommended dosing interval (24 hours), a loading dose is needed to provide steady-state concentrations more rapidly.

10. Pharmacovigilance

For Safety Reference; this study will be conducted consistent with The International Conference on Harmonization Guideline E2A and 21 CFR Part 312 and WHO Guidelines.

Safety assessments will consist of monitoring and recording adverse events; including serious and non-serious adverse events, measurement of protocol-specified safety laboratory assessments, measurement of Protocol-Specified Vital Signs and other Protocol-Specified Measures that are deemed critical to the safety evaluation of the study.

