14.5. Premature Discontinuation of The Study/Premature Close-out of a Site

Sponsor can decide at any time and for any reason to prematurely stop or to interrupt the study; the decision will be communicated in writing to the Investigator.

Similarly, should the Investigator decide to withdraw from the study, she/he will have to immediately inform sponsor in writing.

If appropriate, according to local regulations, Ethic Committee(s) (IRB/IEC) and Competent Authorities should be informed.

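### The interim efficacy analysis after Visit 3 has no endpoint, alpha allocation or decision rule, so the stated 5% error is not protected

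*Combined protocol and SAP*

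**What the plan says.** Section 8.7.3, repeated in the synopsis, places the interim at the point where patients have completed about half of their visits, after Visit 3. It states that "an interim analysis for safety and efficacy will be conducted by an independent data monitoring committee". The same committee follows serious adverse events throughout the study. Nothing is said about which efficacy endpoint is examined, by what test, at what level, or what may be decided.

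The section directly before it, 8.7.2, closes its list of tests with "All tests will be performed on the 5% level of significance". It makes no exception for the interim.

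The sample size in the synopsis and section 8.1 rests on one analysis: "Considering an alpha error of 5% using two-sided 95% CI of Wilcoxon signed-rank test and a study power of 80"%, from which "a sample of 332 patients will be required to detect an effect size of 0.158 between baseline and study endpoint". The interim is not mentioned there.

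The primary endpoints (sections 8.4.1 and 8.5.1) are changes in CDAI and HAQ from baseline to week 36. Visit 3 is at week 12 ± 2 (section 7.2.2). On the expected course of response, section 9.2 says "Improvement in the rheumatoid condition usually starts after 4 to 6 weeks and may further improve up to 4 to 6 months". Section 8.8 defers to a separate SAP only for missing, unused and spurious data, so the question of interim alpha is not deferred anywhere.

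**The concern.** The interim is labelled an efficacy analysis, and the only significance level in the plan is 5% for all tests. Taken together, those two statements permit efficacy to be tested at 5% at week 12 and again at 5% at week 36. If a positive result at either time may be reported as a finding, the chance of a false positive exceeds the 5% on which the study is sized. An efficacy conclusion at the interim would also rest on week-12 data, 24 weeks short of the primary time point and before the further improvement that section 9.2 allows for.

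**Working it through.** **Inputs from the documents.** Two-sided alpha 5%, power 80%, effect size 0.158, 332 evaluable patients (synopsis, section 8.1); all tests at 5% (8.7.2); interim after Visit 3 of 6 (8.7.3); Visit 3 at week 12 ± 2 (7.2.2); primary time point week 36 (8.4.1). **Not in the documents:** the correlation r between the interim and final test statistics. It is assumed, and a range is shown.

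**Step 1. Reproduce the plan's figure.** A paired t-test with two-sided alpha 0.05, power 0.80 and standardised effect 0.158 needs n = 316.3 (noncentral t). Dividing by the asymptotic relative efficiency of the Wilcoxon signed-rank test under normality, 3/π = 0.955, gives 331.3, so 332. This matches. Adding 20% gives 332 × 1.2 = 398.4, the stated 398, rounded to 400. The calculation uses the whole 5% in one test and sets nothing aside for an earlier look.

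**Step 2. Error with two unadjusted looks.** Under no change, let Z1 and Z2 be the interim and final statistics, bivariate normal with correlation r. The probability of at least one significant result is

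1 − P(|Z1| < 1.96 and |Z2| < 1.96).

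| Assumed r | Overall two-sided error, one endpoint |
|---|---|
| 0 | 9.75% (= 1 − 0.95²) |
| 0.3 | 9.5% |
| 0.5 | 9.1% |
| 0.58 (= √(12/36)) | 8.8% |
| 0.71 (= √0.5) | 8.3% |
| 0.8 | 7.8% |
| 0.9 | 7.0% |
| 0.95 | 6.5% |

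A simulation of 2,000,000 pairs at r = 0.7071 gave 8.3%. The value 0.71 is the correlation that 50% information would give. Half of the visits is not the same as half of the information on the week-36 endpoint, which is why the range matters more than the single figure.

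**Step 3. Levels that would hold 5%.** At 50% information, the two-look O'Brien-Fleming boundary has nominal two-sided levels of 0.0052 (interim) and 0.0480 (final). Pocock has 0.0294 at each look. With 332 evaluable patients, the power of the final test is:

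- 80.1% at level 0.05
- 79.6% at level 0.0480
- 73.4% at level 0.0294 (385 patients would be needed for 80%)

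**Step 4. Timing.** The Visit 3 window is weeks 10 to 14 and stated onset is weeks 4 to 6, so the look falls 4 weeks (10 − 6) to 10 weeks (14 − 4) after onset. Four to six months is about 17 to 26 weeks (4 × 52/12 and 6 × 52/12), so the look precedes the end of the stated further improvement. It is 36 − 12 = 24 weeks before the primary time point.

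**The case against.** The strongest reply is that no inflation is shown. Section 8.7.3 mentions no hypothesis test, and the 5% sentence sits in a section that does not refer to the interim. An independent committee may look at efficacy descriptively to weigh benefit against risk. The week-36 error stays at 5% unless an interim result can stop the study or support a claim, and no passage says it can. Nor would the two looks test the same quantity. On the planned milestones, a patient enrolled on 1 September 2017 reaches the earliest Visit 6 (week 34) on about 27 April 2018, while a patient enrolled on 31 December 2017 has the latest Visit 3 (week 14) on 8 April 2018. On schedule, nobody would have week-36 data at the interim. Finally, this is a single-cohort observational study without randomisation.

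Much of this stands. The inflation is conditional, and a reader who infers that efficacy will certainly be tested twice at full 5% goes further than the text. Three other inferences should also be resisted:

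- That the look comes before any expected response. Section 9.2 puts onset at 4 to 6 weeks, so week 12 follows it.
- That section 14.5 ("Sponsor can decide at any time and for any reason to prematurely stop or to interrupt the study") creates an efficacy stopping route. It is a general discontinuation clause that mentions neither the interim nor efficacy.
- That the interim fails because it comes too late to affect recruitment. The plan never gives it that purpose.

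What the reply does not remove is the gap itself. The plan calls the interim an efficacy analysis, sets all tests at 5%, and nowhere says that the look is descriptive or that no conclusion may follow. The descriptive reading is reasonable, but the text does not state it.

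**Conclusion.** The point holds in a conditional form. The plan includes an efficacy look at week 12 with no endpoint, alpha allocation or decision rule, under a blanket 5% rule and a sample size that assumes one test. If an efficacy conclusion is allowed at either look, the overall two-sided error for one endpoint is about 8.3% at r = 0.71, and 6.5% to 9.75% for r from 0.95 to 0; every value in that range exceeds 5%. If no such conclusion is allowed, the final test stays at 5%. The figures assume normal test statistics and an assumed correlation, and they do not count the second primary measure. This should be fixed, but it does not by itself invalidate the week-36 analysis.

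**What to change.** In section 8.7.3 and the synopsis, state that:

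- the interim after Visit 3 is a safety review, and any CDAI or HAQ summaries given to the committee are descriptive only;
- it cannot stop the study for efficacy or support an efficacy claim;
- the full two-sided 5% is kept for the week-36 analysis.

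This takes one paragraph. The sponsor gives up an early efficacy readout; ongoing monitoring of serious adverse events is unaffected.

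If a formal efficacy look is wanted, name its endpoint, justify its information fraction for the week-36 endpoint, and pre-specify an O'Brien-Fleming-type boundary. At 50% information the levels are 0.0052 and 0.0480, and the power of the final test at 332 evaluable patients falls from 80.1% to 79.6%, about half a point. The levels must be recalculated if the information fraction differs. Except the interim from the 5% sentence in section 8.7.2, and state the final level in section 8.1. Either version should be in place before any interim data are seen.

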8.8. Handling of Missing Values

- Procedure for accounting for missing, unused, and spurious data will be explained in the statistical analysis plan (SAP).

9. Treatment

9.1. Product

Each Arthfree 20 mg contains:

Active ingredient: Leflunomide 20 mg

Inactive ingredients: Microcrystalline cellulose, Lactose monohydrate, Maize starch, Anhydrous colloidal silica, Polyvinylpyrrolidone, Croscarmellose sodium, Magnesium stearate.

Each Arthfree 100 mg contains:

Active ingredient: Leflunomide 100 mg

Inactive ingredients: Microcrystalline cellulose, Lactose monohydrate, Maize starch, Anhydrous colloidal silica, Polyvinylpyrrolidone, Croscarmellose sodium, Magnesium stearate.

Patients will be prescribed Arthfree (Leflunomide) at the sole decision of the treating physician.

9.2. Mode of Administration

Arthfree (Leflunomide 20mg)

Study Protocol: EVA_CLEAR_11022017

Dose: 1 tablet once daily, should be swallowed whole with sufficient amounts of liquids. The extent of Leflunomide absorption is not affected if taken with meals. Doses higher than 20 mg/day are not recommended. Improvement in the rheumatoid condition usually starts after 4 to 6 weeks and may further improve up to 4 to 6 months.

Loading dose: a tablet of Leflunomide 100 mg for three days. should be swallowed whole with sufficient amounts of liquids. The extent of Leflunomide absorption is not affected if taken with meals.

Due to the long half-life in patients with rheumatoid arthritis and recommended dosing interval (24 hours), a loading dose is needed to provide steady-state concentrations more rapidly.

10. Pharmacovigilance

For Safety Reference; this study will be conducted consistent with The International Conference on Harmonization Guideline E2A and 21 CFR Part 312 and WHO Guidelines.

Safety assessments will consist of monitoring and recording adverse events; including serious and non-serious adverse events, measurement of protocol-specified safety laboratory assessments, measurement of Protocol-Specified Vital Signs and other Protocol-Specified Measures that are deemed critical to the safety evaluation of the study.

10.1. Definitions

10.1.1. Adverse Events

An adverse event is any untoward medical occurrence in a clinical investigation subject associated with the use of a product or a medical device; the event does not necessarily need to have a causal relationship with the treatment or usage.

Examples of Adverse Events include but are not limited to:

- Abnormal lab test findings of clinical concerns
- Clinically significant symptoms and signs
- Changes in physical examination findings
- Hypersensitivity
- Progression/worsening of underlying disease
- Additionally, they may include the signs or symptoms resulting from:
- Drug Overdose
- Drug Withdrawal
- Drug Abuse
- Drug Misuse
- Drug Interactions
- Drug Dependency

Study Protocol: EVA_CLEAR_11022017

- Exposure During Pregnancy
- Drug Quality Defect That Has Impact On The Patient Safety

10.1.2. Adverse Event of Special Interest

An Adverse Event of Special Interest (AESI) is an AE (Serious or Non-Serious) of scientific and medical concern specific to the Sponsor's Product Or Program, for which ongoing monitoring and rapid communication by the Investigator to the Sponsor may be appropriate. Such events may require further investigation in order to characterize and understand them. AESIs may be added or removed during a study by Protocol Amendment.

In this study, No Adverse Event of Special Interest will be collected.

10.1.3. Serious Adverse Events

A serious adverse event or serious adverse drug reaction is any untoward medical occurrence at any dose that:

- Results In Death
- Is Life-Threatening (Immediate Risk Of Death)
- Requires Inpatient Hospitalization or Prolongation of Existing Hospitalization
- Results In Persistent Or Significant Disability/Incapacity
- Results In Congenital Anomaly/Birth Defect
- Important Medical Event

Medical and Scientific judgment should be exercised in determining whether an event is an important medical event. An important medical event may not be immediately life-threatening and/or result in death or hospitalization. However, if it is determined that the event may jeopardize the subject and/or may require intervention to prevent one of the other adverse event outcomes, the important medical event should be reported as serious.

Examples of such events are intensive treatment in an emergency room or at home for allergic bronchospasm; blood dyscrasias or convulsions that do not result in hospitalization; or development of drug dependency or drug abuse.

10.1.4. Adverse Reaction (Adverse Drug Reaction)

An adverse reaction means any AE caused by a drug. Adverse reactions are a subset of all suspected adverse reactions for which there is reason to conclude that the drug caused the event. This would include all noxious and unintended responses to the MP related to any dose.

10.1.5. Suspected Adverse Reaction

Study Protocol: EVA_CLEAR_11022017 Version Number: Final V2.0/19-Jun-2017

Suspected adverse reaction means any AE for which there is a reasonable possibility that the drug caused the AE. A suspected adverse reaction implies a judgment by the clinical investigator or study sponsor that there is a reasonable possibility that the AE has a causal relationship with the Investigational Product, though with a lesser degree of certainty about causality, compared to the use of the term "adverse reaction" (or "adverse drug reaction") as defined above

For the purposes of U.S. IND safety reporting, the meaning of 'Reasonable Possibility' is clarified in FDA's recent changes to CFR 312 by the following examples of types of evidence that would suggest a causal relationship between the drug and the AE, such as:

- A single occurrence of an event that is uncommon and known to be strongly associated with drug exposure (e.g., angioedema)
- One or more occurrences of an event that is not commonly associated with drug exposure, but is otherwise uncommon in the population exposed to the drug (e.g., tendon rupture)
- An aggregate analysis of specific events observed in a clinical trial (such as known consequences of the underlying disease or condition under investigation or other events that commonly occur in the study population independent of drug therapy) that indicates those events occur more frequently in the drug treatment group than in a concurrent or historical control group.

10.1.6. Unexpected Adverse Drug Reaction

An AE or suspected adverse reaction is considered "Unexpected" if it is not listed in the Approved Product Label (for regulatory-approved, commercially available products) or in the investigator brochure, or is not listed at the specificity or severity that has been observed in a serious adverse event at hand; or, if an investigator brochure is not required or available, is not consistent with the risk information described in the general investigational plan or elsewhere in the available information about the MP. "Unexpected," as used in this context, also refers to AEs or suspected adverse reactions that are mentioned in the investigator brochure as occurring with the given class of drugs or may be anticipated from the pharmacological properties of the drug, but are not specifically mentioned as occurring with the particular MP under investigation.

10.1.7. Abnormal Test Findings

Treatment-emergent laboratory test abnormalities considered to be of clinical concern should be recorded as AEs in the CRF

The criteria for determining whether an abnormal objective test finding should be reported as an adverse event are as follows:

- 1. Test result is associated with accompanying symptoms, and/or
- 2. Test result requires additional diagnostic testing or medical/surgical intervention, and/or

Study Protocol: EVA_CLEAR_11022017 Versi

- 3. Test result leads to a change in study dosing or discontinuation from the study, significant additional concomitant drug treatment, or other therapy, and/or
- 4. Test result is considered to be an adverse event by the investigator or sponsor.

Merely repeating an abnormal test, in the absence of any of the above conditions, **does not** constitute an adverse event.

Any abnormal test result that is determined to be **an error** does not require reporting as an adverse event.

10.1.8. Hospitalization

Adverse events reported from studies associated with hospitalization or prolongations of hospitalization are considered serious. Any initial admission (even if less than 24 hours) to a healthcare facility meets these criteria. Admission also includes transfer within the hospital to an acute/intensive care unit (e.g., from the psychiatric wing to a medical floor, medical floor to a coronary care unit, neurological floor to a tuberculosis unit).

Hospitalization does not include the following:

- Rehabilitation facilities
- Hospice facilities
- Respite care (e.g., caregiver relief)
- Skilled nursing facilities
- Nursing homes
- Routine emergency room admissions
- Same day surgeries (as outpatient/same day/ambulatory procedures).

Hospitalization or prolongation of hospitalization in the absence of a precipitating, clinical adverse event is not in itself a serious adverse event. Examples include:

- Admission for treatment of a preexisting condition not associated with the development of a new adverse event or with a worsening of the preexisting condition (e.g., for work-up of persistent pre-treatment lab abnormality)
- Social admission (e.g., subject has no place to sleep)
- Administrative admission (e.g., for yearly physical exam)
- Protocol-specified admission during a study (e.g., for a procedure required by the study protocol)
- Optional admission not associated with a precipitating clinical adverse event (e.g., for elective cosmetic surgery)
- Pre-planned treatments or surgical procedures should be noted in the baseline documentation for the entire protocol and/or for the individual subject.

Diagnostic and therapeutic non-invasive and invasive procedures, such as surgery, should not be reported as adverse events. However, the medical condition for which the procedure was performed should be reported if it meets the definition of an adverse event. For example, an acute appendicitis that begins during the adverse event reporting period should be reported as the adverse event, and the resulting appendectomy should be recorded as treatment of the adverse event.

